## 7. CORRELATIVE/SPECIAL STUDIES

Patients with available tumor tissue will have EGFR exon 20 analyzed by direct sequencing if they have not already had this testing. The purpose of this is to know the exact exon 20 mutation for all patients on the study, variations in outcome by mutation type can be explored. Some of the participating institutions use direct sequencing already as their clinical test to identify these patients, while some use a sizing assay that does not provide the exact insertion or insertion/deletion mutation. Patients without available tumor tissue will be eligible to participate in the study and will not have to undergo a biopsy.

## 7.1 Pharmacokinetic Studies

N/A

## 8. STUDY CALENDAR

### Table 6. Required Data

|  | Baseline       | Cycle 1 |   |   | Cycle 2 |    |   | Subsequent cycles |    |                 | End of Treatment | 28 Day Safety Visit | Tumor FU              | Survival FU               | End of Study |     |
|--|----------------|---------|---|---|---------|----|---|-------------------|----|-----------------|------------------|---------------------|-----------------------|---------------------------|--------------|-----|
| Day of Cycle   | -21 to -1      | 1       | 2 | 3 | 8       | 15 | 1 | 8                 | 15 | 1               | 8                | 15                  | ≤ 7 days of last dose | 28 (±7) days of last dose | N/A          | N/A |
| Informed consent   | X              |         |   |   |         |    |   |                   |    |                 |                  |                     |                       |                           |              |     |
| Inclusion/Exclusion Criteria                                     | X              |         |   |   |         |    |   |                   |    |                 |                  |                     |                       |                           |              |     |
| Collection of baseline required demographic and clinical data    | X              |         |   |   |         |    |   |                   |    |                 |                  |                     |                       |                           |              |     |
| Vitals signs and ECOG Performance status             | X              | X       | X | X | X       | X  | X | X                 | X  | X               | X                | X                   |                       |                           |              |     |
| Physical Exam  | X              | X       | X | X | X       | X  | X | X                 | X  | X               | X                | X                   |                       |                           |              |     |
| 12-lead ECG    | X              | X       | X | X | X       | X  | X | X                 | X  | X               | X                | X                   |                       |                           |              |     |
| Cardiac imaging (MUGA or ECHO)                                   | X              |         |   |   |         |    |   |                   |    |                 |                  |                     | X                     |                           |              |     |
| Hematology and biochemistry labs                     | X              | X       | X | X | X       | X  | X | X                 | X  | X               | X                | X                   |                       |                           |              |     |
| Coagulation labs   | X              | X       |   |   |         | X  |   |                   |    | X  |                  | X                   |                       |                           |              |     |
| Urinalysis   | X              | X       |   |   |         | X  |   |                   |    | X  |                  | X                   |                       |                           |              |     |
| Eye Exam   | X  |         |   |   |         |    |   |                   |    | X   |                  | X       |                       |                           |              |     |
| AUY922 IV infusion                                   | X              |         | X | X | X       | X  | X | X                 | X  | X               | X                |                     |                       |                           |              |     |
| Concomitant Medications  | X              |         |   |   |         |    |   |                   |    |                 |                  | Ongoing             | X                     |                           |              |     |
| Adverse Events   | X              |         |   |   |         |    |   |                   |    |                 |                  | Ongoing             | X                     | X                         |              |     |
| Radiological assessment of tumor – CT/MRI            | X              |         |   |   |         |    |   |                   |    |                 |                  |                     | X         |                           |              |     |
| Survival   |                |         |   |   |         |    |   |                   |    |                 |                  |                     | X                     | X                         | X            |     |
| Tumor sample for mutation and amplification testing  | X              |         |   |   |         |    |   |                   |    |                 |                  |                     | X                     | X                         | X            |     |

1. Vital signs – During treatment period, vital signs will be performed pre-dose (including temperature, respiratory rate, blood pressure, pulse, weight and ECOG PS) and immediately post-dose infusion (including temperature, respiratory rate, blood pressure and pulse).
2. ECG- Please refer to Table 3 for detailed schedule of ECGs.
3. In women of child-bearing potential, a serum pregnancy test must be obtained prior (within 14 days) to the first administration of AUY922. CHEMISTRY: BUN, Creatinine, Glucose, Total Protein, Albumin, AST/SGOT, ALT/SGPT, Total Bilirubin, Alkaline Phosphatase, Magnesium, Calcium, Sodium, Potassium, Phosphorous. HEMATOLOGY: CBC with differential
4. Standard ophthalmologic assessments will be required at baseline and follow-up exams will be conducted at the time when visual symptoms are reported (if any), at cycle 3 day 1 if no visual symptoms are reported, and at study discontinuation. There is a +/- 7 day window allowed for eye exam at Cycle 3 day 1
5. One should aim to administer AUY922 on the same day each week, but there is a +/- 2 day window allowed to account for holidays, inclement weather, transportation difficulties, etc. For patients who are unable to tolerate the protocol-specified dosing schedule, schedule adjustments are permitted. This includes the ability to skip a week of dosing if needed up to once per cycle. Patients who continue treatment beyond progression can skip up to two infusions per cycle if needed after discussion between the treating MD and the overall PI of the study.
6. A CT scan with contrast of the chest, abdomen, and pelvis will be performed on patients at baseline (screening) -30 to -1 days prior to study drug administration. The same type of imaging modality (CT with contrast or MRI) used at screening must be used for all subsequent follow-up assessments. Follow-up CT/MRI scans will be performed every 6 weeks ( $\pm$ 7 days) from registration.
7. In the event that a patient is discontinued from treatment for any reason other than disease progression, an end of treatment CT/MRI is recommended to be performed if the last scan was conducted  $\geq$  4 weeks previously. Such patients who discontinue study treatment for reasons other than disease progression should be re-staged every 12 weeks ( $\pm$ 7 days) until start of another anti-cancer treatment.
8. Patients will be followed for survival every 3 months after discontinuing the trial. Follow-ups may be conducted over the telephone.
9. If available, tumor samples will be sequenced for EGFR exon 20 mutation.
10. For patients who miss a D1 visit of any cycle (as allowed per protocol,) any missed day 1 assessments (for example, coagulation studies and urinalysis) will be performed at the next clinic visit.

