### 3. PARTICIPANT SELECTION

#### 3.1 Eligibility Criteria

Participants must meet the following criteria on screening examination to be eligible to participate in the study:

- 3.1.1 Participants must have histologically or cytologically confirmed stage IV or recurrent non-small cell lung cancer with a documented exon 20 insertion mutation in *EGFR* (exon 20 insertion/deletion and deletion mutations will also be allowed)
- 3.1.2 Participants must have measurable disease by RECIST 1.1
- 3.1.3 Patients must have received at least one prior line of therapy for their advanced lung cancer but there is no restrictions on the maximum number of prior therapies allowed.
- 3.1.4 Age  $\geq$  18 years.
- 3.1.5 Life expectancy  $\geq$  12 weeks.
- 3.1.6 ECOG performance status  $\leq$  2 (see Appendix A)
- 3.1.7 Participants must have normal organ and marrow function as defined below:
  - Hematologic:
    - Absolute Neutrophil Count (ANC)  $\geq 1.5 \times 10^9/L$
    - Hemoglobin (Hgb)  $\geq 8 \text{ g/dL}$
    - Platelets (plt)  $\geq 100 \times 10^9/L$
  - Biochemistry:
    - Potassium within normal limits or correctable with supplements
    - Magnesium  $>$  LLN or correctable with supplements
    - Calcium (after correction for albumin level)  $>$  LLN or correctable with supplements
  - Liver and Kidney Functions
    - AST/SGOT and ALT/SGPT  $\leq 3.0 \times$  Upper Limit of Normal (ULN) or  $\leq 5.0 \times$  Upper Limit of Normal (ULN) if liver metastases are present
    - Serum bilirubin  $\leq 1.5 \times$  ULN
    - Serum creatinine  $\leq 1.5 \times$  ULN or 24-hour clearance  $\geq 50 \text{ ml/min}$

3.1.8 The effects of AUY922 on the developing human fetus are unknown. For this reason women of child-bearing potential and men must agree to use adequate contraception (hormonal or barrier method of birth control; abstinence) prior to study entry and for the duration of study participation. Should a woman become pregnant or suspect she is pregnant while participating in this study, she should inform her treating physician immediately. In addition, women of child-bearing potential must have a documented negative serum pregnancy test. The serum pregnancy test must be obtained prior to the first administration of AUY922 ( $\leq$  72 hours prior to dosing) in all pre-menopausal women and women  $<2$  years after the onset of menopause.

3.1.9 Ability to understand and the willingness to sign a written informed consent document.

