## 3.2 Exclusion Criteria

Participants who exhibit any of the following conditions at screening will not be eligible for admission into the study.

3.2.1 Participants may not have had other anti-neoplastic therapies within the following timelines:

- Radiation within 2 weeks
- Cytotoxic chemotherapy or monoclonal antibodies within 2 weeks, if all treatment-related toxicities have resolved to  $\leq$  grade 1 prior to starting study treatment.
- EGFR tyrosine kinase inhibitor within 2 weeks
- Any other small molecule inhibitor within 2 weeks or 5 half-lives of the compound, whichever is shorter
- Experimental treatment of any type within 30 days

3.2.2 Participants may not be currently receiving any other experimental agents.

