## **5.1 Pre-treatment Criteria**

### **5.1.1 Cycle 1, Day 1**

The patient should continue to meet all eligibility criteria on C1D1, as they did during the screening period.

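### The reference scan may be up to 30 days old and need not follow the last prior therapy, so tumour change from before dosing can be scored as an outcome on AUY922

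*Combined protocol and SAP*

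**What the plan says.** **Scan timing.** Table 6, footnote 6 allows the CT "at baseline (screening) -30 to -1 days prior to study drug administration". The Baseline column of the same table runs from day -21 to day -1, and the footnote widens it for the scan.

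**Prior therapy.** Every patient is pre-treated: "Patients must have received at least one prior line of therapy for their advanced lung cancer" (section 3.1.3). Section 3.2.1 sets these exclusions by type of treatment:
- Radiation, chemotherapy, antibodies and EGFR inhibitors all carry the same 2-week limit. The entry for radiotherapy, for example, reads "Radiation within 2 weeks". The chemotherapy and antibody entry adds a condition on resolved toxicity.
- The remaining targeted drugs have a limit that can be shorter: "Any other small molecule inhibitor within 2 weeks or 5 half-lives of the compound, whichever is shorter".
- Investigational agents have a longer one: "Experimental treatment of any type within 30 days".

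None of these bullets says which day the interval is counted from. The lead sentence of section 3.2 refers to conditions present at screening. Section 5.1.1 adds: "The patient should continue to meet all eligibility criteria on C1D1". It does not call for a new scan.

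**Use of the scan.** Section 9.1.3.1 measures PR against the baseline sum of diameters and PD against the smallest sum on study, and any new lesion is PD. Section 9.1.4 counts the duration of SD from the start of treatment.

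**Decision rule.** Section 13.2 counts responses plus SD of at least 3 months. Stage 2 opens on 1 success in 10 patients, and the final go needs 4 in 29. The null rate is 5%, the target 20%, the stated type I error 0.047 and the stated type II error 0.199.

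**The concern.** In a single-arm trial the baseline scan is the only comparator, so it should describe the disease as it stood when AUY922 began. Here the scan can predate the end of the previous treatment. Nothing found in the plan requires the scan to follow the last prior therapy, to be repeated, or to be preceded by documented progression on the prior line.

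Errors can then run both ways. Shrinkage produced by the earlier treatment after the scan is credited to AUY922, and can turn true SD into PR or true PD into SD. Growth or new lesions between the scan and the first dose are charged to AUY922, and can turn SD into PD. With a bar of 4 successes in 29, and 1 in 10 at stage 1, a single reclassified patient can change the decision if the count lies next to the bar.

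**Working it through.** **1. Size of the window** (footnote 6 and section 3.2.1). Overlap = age of scan at dosing minus time off therapy at dosing.
- 2-week agents, counted back from dosing: 30 - 14 = 16 days.
- Other small molecules with 5 half-lives shorter than 14 days: 30 - 5 x half-life, so more than 16 days.
- Experimental treatment: 30 - 30 = 0 days.
- If the scan had to fall in the day -21 to -1 column instead: 21 - 14 = 7 days.
- If the 2 weeks are counted back from an eligibility visit s days before dosing: 30 - (14 + s) = 16 - s days. Overlap remains for s up to 15 and disappears from s = 16. If they are counted back from the scan itself, there is no overlap.

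**2. What shifts.** SD duration does not: its clock starts at treatment (section 9.1.4), so an old scan adds no SD time. Only the reference size, and the set of lesions regarded as already present, are affected.

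**3. The plan's own figures** (section 13.2). With X ~ Bin(10, p) and Y ~ Bin(19, p),

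P(go) = sum over x = 1 to 10 of P(X = x) * P(Y >= 4 - x).

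At p = 0.05:
- x = 1: 0.3151 * 0.0665 = 0.0210
- x = 2: 0.0746 * 0.2453 = 0.0183
- x = 3: 0.0105 * 0.6226 = 0.0065
- x >= 4: 0.0010

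The sum is 0.0468, which reproduces 0.047. At p = 0.20 the same formula gives 0.8011, so the type II error is 0.1989, which reproduces 0.199.

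**4. Sensitivity to misattribution (illustration only).** Let d be the net number of successes gained or lost per 29 patients, so that the observed rate at a true 5% is 0.05 + d/29. The values of d are assumptions.

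| d | observed rate | P(go) |
|---|---|---|
| -0.5 | 0.0328 | 0.012 |
| 0 | 0.0500 | 0.047 |
| +0.5 | 0.0672 | 0.110 |
| +1 | 0.0845 | 0.197 |

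For scale, 29 * 0.95 = 27.55 true non-successes are expected, so d = +1 needs a net 1/27.55 = 3.6% of them converted. Expected true successes are 29 * 0.05 = 1.45, so d = -0.5 needs a net 0.5/1.45 = 34% of them lost.

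The loss side matters more under the target rate. If 5% or 10% of true successes are scored as PD, the observed rate is 0.20 * 0.95 = 0.19 or 0.20 * 0.90 = 0.18, and power falls from 0.801 to 0.768 or 0.730.

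**The case against.** **The washout anchor is not stated.** Section 3.2 speaks of screening, and footnote 6 calls the scan a screening procedure. A site could reasonably hold that a patient still on chemotherapy at the scan fails 3.2.1. This stands: the 16 days depend on counting from dosing. It does not close the gap, because the text does not impose the stricter reading and overlap survives whenever the eligibility visit is close enough to dosing (step 1).

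**Irradiated lesions are already restricted.** Section 9.1.1 treats a lesion in a previously irradiated area as non-measurable unless it has progressed. This largely stands, since the ordinary sense is progression after the irradiation. What is left uncovered is a lesion that was progressing before enrollment, was chosen as a target, and was irradiated after the baseline scan.

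**The success definition filters carry-over.** PR needs a 30% decrease, Table 7 provides for confirmation at 4 weeks or more, and SD must last 3 months from start of treatment. PD is judged from the smallest sum on study, so transient shrinkage makes later PD easier to reach. These points reduce the problem. They do not remove it, because confirmation uses the same baseline. Central measurement (section 9.1.6) addresses reader bias and not scan timing.

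**The size is assumed.** This stands in full. A reader might infer from the table that the true type I error is near 0.197, or that the trial leans toward a go. The documents support neither: they give no carry-over rate, and losses are as possible as gains. Nor is it right that all prior therapy may stop 2 weeks before dosing, since experimental agents need 30 days.

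**Conclusion.** The gap is real but modest. The plan permits a reference scan taken before prior therapy has ended, by up to about 16 days if the 2 weeks are counted back from dosing, and by more for some small molecules. Tumour change unrelated to AUY922 can therefore enter the counts of 10 and 29 as success or failure. It does so only through the reference size and new lesions, not through a longer SD.

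How often this would happen, and which way it would tip the result, cannot be learned from the documents. The range 0.012 to 0.197 shows how sensitive the 4-of-29 rule is to a net shift between -0.5 and +1 success; it does not estimate the bias. The point is a worthwhile tightening of the measurement rule. It does not show that the design or its stated error rates are wrong.

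**What to change.** 1. **Table 6, footnote 6:** require the baseline scan to be taken after the last dose of prior systemic anticancer therapy, timed within the existing washout. The washout intervals need not change.
2. **Section 9.1.1:** state that a lesion irradiated after the baseline scan cannot be a target lesion.
3. **Section 13.6:** for any patient whose baseline scan nevertheless predates the end of prior therapy, pre-specify a two-way sensitivity analysis of the 10- and 29-patient counts. In one direction, recode that patient's apparent success as a non-success. Separately, recode early PD as a success, with early PD defined in advance (for example, PD at the 6-week assessment). A one-way analysis would test only for false successes.
4. **Data:** record the scan date and the last-therapy date. The latter is needed to verify 3.2.1, but the plan does not list it as a separate data item.

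**Cost:** amendment wording and a small analysis. Some screening scans must be scheduled later, with less room where a small molecule has a washout shorter than 2 weeks. Items 2 to 4 need no extra scan. N = 29, alpha and power do not change.

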## **4. REGISTRATION PROCEDURES**

### **4.1 General Guidelines for DF/HCC and DF/PCC Institutions**

Institutions will register eligible participants with the DF/HCC Quality Assurance Office for Clinical Trials (QACT) central registration system. Registration must occur prior to the initiation of therapy. Any participant not registered to the protocol before treatment begins will be considered ineligible and registration will be denied.

A member of the study team will confirm eligibility criteria and complete the protocol-specific eligibility checklist.

Following registration, participants may begin protocol treatment. Issues that would cause treatment delays should be discussed with the Principal Investigator. If a participant does not receive protocol therapy following registration, the participant's protocol status must be changed. Notify the QACT Registrar of participant status changes as soon as possible.

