#### 9.1.4 Duration of Response

**Duration of overall response:** The duration of overall response is measured from the time measurement criteria are met for CR or PR (whichever is first recorded) until the first date that recurrence or PD is objectively documented, taking as reference for PD the smallest measurements recorded since the treatment started.

**Duration of overall complete response:** The duration of overall CR is measured from the time measurement criteria are first met for CR until the first date that recurrent disease is objectively documented.

**Duration of stable disease:** Stable disease is measured from the start of the treatment until the criteria for progression are met, taking as reference the smallest measurements recorded since the treatment started.

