#### 9.1.5 Progression-Free Survival

Progression-Free Survival (PFS) is defined as the duration of time from start of treatment to time of objective disease progression.

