### **13.7 Analysis of Progression-Free and Overall Survival**

Progression-Free Survival (PFS) will be defined as the duration of time from start of treatment to time of objective disease progression or death. Overall survival (OS) will be defined as the duration of time from start of treatment until death. Analysis will be performed using the Kaplan-Meier method. All patients will be evaluable for survival endpoints.

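### Restaging scans are timed from registration while SD duration and PFS run from first dose, so a longer start delay makes SD of 3 months or more easier to reach

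*Combined protocol and SAP*

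**What the plan says.** Footnote 6 to Table 6 (Section 8) sets the imaging schedule: "Follow-up CT/MRI scans will be performed every 6 weeks ( $\pm$ 7 days) from registration". Section 9.1 repeats the 6-week interval without a time zero, so nothing overrides the footnote. The same footnote times the baseline CT relative to study drug administration, so it uses two anchors.

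The endpoints that these scans feed start elsewhere. Section 9.1.4: "Stable disease is measured from the start of the treatment until the criteria for progression are met". Section 9.1.5: "Progression-Free Survival (PFS) is defined as the duration of time from start of treatment to time of objective disease progression". Section 13.7 likewise defines PFS as "the duration of time from start of treatment to time of objective disease progression or death".

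Section 4.1 requires registration before therapy and then says "Following registration, participants may begin protocol treatment". It gives no number of days, and asks only that issues causing delay be discussed with the Principal Investigator. Table 6 puts consent and the eligibility check in the Day −21 to −1 column, and Section 4.2 puts both before registration.

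Section 13.2 counts SD lasting at least 3 months as a success alongside response, at stage 1 (at least 1 of 10) and at the end (at least 4 of 29).

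**The concern.** Progression is normally established by a scan, so the date of documented progression depends on when scans happen. If scans are counted from registration and SD duration from first dose, each day of start delay moves every nominal scan one day earlier on the treatment clock.

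Take a patient whose disease progresses on treatment day 80. Dosed on the day of registration, the patient has nominal scans on days 42, 84 and 126. Progression is documented on day 84, short of 3 months: a failure. Dosed 14 days after registration, the patient has scans on days 28, 70 and 112. SD is seen on day 70 and progression on day 112: a success. Both were scanned on schedule and had the same disease course.

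At nominal timing the effect runs one way, towards success, and it enters both Simon decisions. PFS also inherits assessment times that differ between patients on the treatment clock.

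**Working it through.** **Inputs from the documents.** Scan interval 42 days from registration (Table 6, footnote 6). SD and PFS counted from start of treatment (9.1.4, 9.1.5, 13.7). Null rate 0.05, target 0.20, stop if 0 of 10, pass if at least 4 of 29, stated error rates 0.047 and 0.199 (13.2).

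**Assumptions.** 3 months = 91 days, since the documents do not define it (90 or 92 gives the same nominal result). SD lasts until the scan that documents progression. Time to progression is exponential. The gap g runs from 0 to 21 days.

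**Step 1: reproduce the design.** P(pass | p) = Σ over x = 1 to 10 of C(10,x) pˣ(1−p)^(10−x) × P(Y ≥ 4−x), with Y ~ Bin(19, p).

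At p = 0.05: 0.3151×0.0665 + 0.0746×0.2453 + 0.0105×0.6226 + 0.0010 (x ≥ 4) = 0.0468. At p = 0.20 the sum is 0.8011, so beta = 0.1989. Both stated figures are reproduced.

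**Step 2: scan days on the treatment clock.** Scan k falls on day 42k − g.

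| g | Scan 2 | Scan 3 |
|---|---|---|
| 0 | 84 | 126 |
| 7 | 77 | 119 |
| 14 | 70 | 112 |
| 21 | 63 | 105 |

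For every g from 0 to 21, progression found at scan 2 comes before day 91 and progression first found at scan 3 comes after it. The working hurdle is therefore to be progression-free on day 84 − g.

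**Step 3: effect on the decision under the null.** Set success at g = 0 to 5% and suppose that no success is a RECIST response. Then p(g) = 0.05^((84−g)/84); for example, at g = 14, 0.05^(70/84) = 0.0824. Put each p(g) into the Step 1 formula, with every patient at the same gap:

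| g | p(g) | P(pass) |
|---|---|---|
| 0 | 0.0500 | 0.047 |
| 7 | 0.0642 | 0.097 |
| 14 | 0.0824 | 0.185 |
| 21 | 0.1057 | 0.324 |

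**Step 4: gaps that vary between patients.** Average p(g) over whole days with equal weight, then apply the rule. For 0–7 days the mean is 0.057 and P(pass) 0.069; for 0–14 days, 0.065 and 0.100; for 0–21 days, 0.075 and 0.145.

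**Step 5: other readings.**
- (a) Half of the null successes are responders unaffected by timing: p(g) = 0.025 + 0.975 × (0.025/0.975)^((84−g)/84).
- (b) SD must be seen on a scan at or after day 91, so scan 3 decides: p(g) = 0.05^((126−g)/126).

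| g | (a) p, P(pass) | (b) p, P(pass) |
|---|---|---|
| 7 | 0.0589, 0.076 | 0.0591, 0.077 |
| 14 | 0.0710, 0.127 | 0.0697, 0.121 |
| 21 | 0.0875, 0.214 | 0.0824, 0.185 |

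The shifts are smaller but in the same direction.

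**Step 6: scans timed from first dose.** Scan 2 is nominally on day 84 for everyone, p no longer depends on g, and the Step 1 figures are kept under this calibration.

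**The case against.** A reader might infer that the gap is unlimited, because Section 4.1 names no limit. The documents do not support that. Consent and eligibility fall in the Day −21 to −1 window and precede registration, so a calendar that is followed allows about 21 days at most. Reaching 21 would need consent, screening and registration all on Day −21. The 21-day row is an upper bound, not an expected case.

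A second tempting step is to assume a median time to progression of 60 to 120 days, find that a 14-day gap reclassifies several percent of patients, and set that against the 5% null. Those medians imply success at day 84 of 2^(−84/60) = 38% to 2^(−84/120) = 62%, and a pass probability of at least 0.99 with no gap at all. They cannot be compared with the null. A 5% rate at day 84 implies an exponential median of 84 × ln 2 / ln 20 ≈ 19 days, which is why the working is calibrated to the null directly.

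The strongest remaining objection is that the ±7 day window already permits the same kind of flip. Even with scans timed from first dose, the day-80 patient is a success if scan 2 falls on day 77 and a failure if it falls on day 84. This stands: for gaps up to 7 days the shift is no larger than the window, and re-anchoring alone does not settle what establishes 3 months. But the window can move a scan either way, whereas a start delay only moves it earlier and adds to the window.

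It is also true that the documents give no gap distribution, so differences between sites are conjecture. SD duration does not enter the response rate of Section 13.6, and PFS is a single-arm estimate with no between-arm contrast to bias.

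**Conclusion.** The point holds as a mismatch of time origins. Scans are counted from registration, the SD and PFS clocks from first dose, and no other text reconciles them. At nominal timing, a longer start delay makes it easier to count as SD of 3 months or more, and so to pass both Simon decisions.

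The size is uncertain. The illustrative inflation of the 0.047 error is to 0.069–0.145 with evenly spread gaps, and to 0.324 only if every patient waits the full 21 days. These figures rest on an exponential curve, 91 days for 3 months, SD lasting until progression is documented, and no responders among the null successes. Alternatives (a) and (b), compared at the same common gap, give smaller shifts in the same direction.

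A reader should not conclude that the stated 0.047 and 0.199 are miscalculated; both reproduce. The issue is what the 5% and 20% rates measure when the assessment day varies with start delay. This is a cheap improvement to a go/no-go endpoint, not a defect that invalidates the design.

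**What to change.** Change Table 6 footnote 6 so that follow-up scans are due every 6 weeks (±7 days) from Cycle 1 Day 1, and use the same anchor in Section 9.1.

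In Section 13.2, state which scan or treatment day establishes SD lasting at least 3 months. The ±7 day window puts scan 2 anywhere from day 77 to day 91, so some ambiguity around day 84 remains without that definition.

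The cost is a minor amendment and sites scheduling scans from Cycle 1 Day 1 instead of registration. No extra scans are needed, and the sample size and decision thresholds are unchanged.
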